 - For revised IWG, a nodal lesion >1.5 cm in longest diameter or >1.0 cm in short axis, or an extranodal lesion ≥ 1 cm in 2 dimensions.
- 7. Have an ECOG Performance Status of 0 or 1.
- 8. Demonstrate adequate organ function as defined by Table 1.
 - All screening labs should be performed within 7 days prior to treatment initiation.

Protocol/Amendment No.: 001-08

9. A female participant is eligible to participate if she is not pregnant or breastfeeding, and at least one of the following conditions applies:

Is not a WOCBP

OR

- Is a WOCBP and using a contraceptive method that is highly effective (with a failure rate of <1% per year), with low user dependency, or be abstinent from heterosexual intercourse as their preferred and usual lifestyle (abstinent on a long-term and persistent basis), as described in Section 5.7.2 during the intervention period and for at least 130 days after the last dose of study intervention and agrees not to donate eggs (ova, oocytes) to others or freeze/store for her own use for the purpose of reproduction during this period. The investigator should evaluate the potential for contraceptive method failure (ie, noncompliance, recently initiated) in relationship to the first dose of study intervention.
- A WOCBP must have a negative highly sensitive pregnancy test (urine or serum) within 24 hours before the first dose of study intervention. If a urine test cannot be confirmed as negative (eg, an ambiguous result), a serum pregnancy test is required. In such cases, the participant must be excluded from participation if the serum pregnancy result is positive.
- Additional requirements for pregnancy testing during and after study intervention are located in Section 5.7.2.
- The investigator is responsible for review of medical history, menstrual history, and recent sexual activity to decrease the risk for inclusion of a woman with an early undetected pregnancy.
- Contraceptive use by women should be consistent with local regulations regarding the methods of contraception for those participating in clinical studies.
- 10. Male subjects are eligible to participate if they agree to the following during the intervention period and for at least 130 days after the last dose of study intervention:
 - Refrain from donating sperm

PLUS either:

• Be abstinent from heterosexual intercourse as their preferred and usual lifestyle (abstinent on a long-term and persistent basis) and agree to remain abstinent

OR

• Must agree to use contraception unless confirmed to be azoospermic (vasectomized or secondary to medical cause [Section 5.7.2]) as detailed below:

Agree to use a male condom plus partner use of an additional contraceptive method when having penile-vaginal intercourse with a WOCBP who is not currently pregnant. Note: Men with a pregnant or breastfeeding partner must agree to remain abstinent from penile-vaginal intercourse or use a male condom during each episode of penile-vaginal penetration.

Protocol/Amendment No.: 001-08

Contraceptive use by men should be consistent with local regulations regarding the methods of contraception for those participating in clinical studies.

- 11. HIV-infected subjects must meet these additional criteria:
 - Have HIV-1 infection documented by any licensed rapid HIV test or HIV E/CIA test kit at any time prior to study entry (Day 1) and confirmed by a licensed Western blot or a second antibody test by a method other than the initial rapid HIV and/or E/CIA, or by HIV-1 p24 antigen, or plasma HIV-1 RNA VL.
 - Have well-controlled HIV on ART, defined as:
 - must have a CD4+ T cell count >350 cells/mm3 at time of screening;
 - must have achieved and maintained virologic suppression defined as confirmed HIV RNA level below 50 or the LLOQ (below the limit of quantification) using the locally available assay at the time of screening and for at least 12 weeks prior to screening;
 - must have been on a stable regimen, without changes in drugs or dose modification, for at least 4 weeks prior to study entry (Day 1).

5.1.3 Subject Inclusion Criteria for Part II - Expansion Cohorts

- 1. Be ≥ 18 years of age on day of signing informed consent.
- 2. Voluntarily agreed to participate by providing documented informed consent. The subject may also provide consent for Future Biomedical Research. However, the subject may participate in the main trial without participating in Future Biomedical Research.
- 3. Have at least one measurable lesion which is amenable to injection. Tumor lesions situated in a previously irradiated area are considered measurable if progression has been demonstrated in such lesions. Intratumoral injection for cutaneous lesions may be performed via visual inspection. Intratumoral injection for subcutaneous lesions may be performed via ultrasound guidance or via palpation. This injectable lesion must meet one of the following criteria:
 - A cutaneous or subcutaneous lesion ≥1 cm in longest diameter for solid tumors, or ≥1.5 cm in short axis for a nodal lesion in solid tumor subjects. The longest diameter for an injectable lesion must be ≤10 cm for both solid tumors and nodal lesions in solid tumor subjects.
 OR
 - Multiple coalescing, superficial lesions which in aggregate have a longest diameter of ≥ 1 cm and ≤ 10 cm.

Protocol/Amendment No.: 001-08

4. In subjects to be treated by liver IT injection, has metastatic liver involvement that does not exceed one-third of the total liver volume. Hepatocellular carcinoma subjects are excluded from eligibility for intratumoral liver injection. In addition, has at least one injectable liver lesion that meets both the following conditions:

- The injectable liver lesion is amenable to image-guided intratumoral injection and biopsy via ultrasound guidance or cross-sectional imaging (CT/MRI). AND
- Injectable lesion(s) must be ≥1 cm in longest diameter and ≤10 cm in longest diameter.
- 5. Subjects with any one of the following solid malignancies who meet all listed conditions of eligibility for an expansion cohort:
 - Cohort A: HNSCC of the oral cavity, oropharynx, hypopharynx, or larynx; anti-PD-1/PD-L1 refractory (see Table 2) metastatic or recurrent. Subjects may not have a primary tumor site of the nasopharynx (any histology).
 - Have histologically confirmed Stage III, IVa, or IVb disease per TNM staging, AJCC Eighth edition, with recurrent or persistent disease after definitive chemoradiation, deemed unresectable and considered refractory to both platinum-based combination chemotherapy and anti-PD-1/PD-L1 antibody therapy.

OR

- Have histologically confirmed Stage IVc disease per TNM staging, AJCC Eighth edition, considered refractory to platinum-based combination chemotherapy and anti-PD-1/PD-L1 antibody therapy.
- Cohort B: Either anti-PD-1/PD-L1 treatment-naïve or refractory (see Table 2) TNBC
 - o Have confirmed unresectable locally advanced or metastatic TNBC as locally determined according to the ASCO-CAP guidelines [27] on a newly obtained core or excisional biopsy from a not previously irradiated, tumor lesion.
 - Have received at least one prior systemic treatment for breast cancer and have documented disease progression on or after their most recent therapy.
 - O Have been previously treated with an anthracycline and/or taxane in the (neo)adjuvant or metastatic setting unless there was a medical contraindication to this treatment regimen.
 - o Have LDH <2.5 × ULN [28] [29] [30].
- Cohort C: Other anti-PD-1/PD-L1 treatment-naïve solid tumors with liver metastases (including pancreatic cancer, non-MSI-H CRC, and other solid tumors. MSI-H status is to be determined by local testing).
 - Have histologically or cytologically confirmed Stage IV solid tumor that is not surgically resectable.

Protocol/Amendment No.: 001-08

Table 2 Anti-PD-1/PD-L1 Antibody Refractory Definition

Patients must have progressed on treatment with an anti-PD-1/PD-L1 monoclonal antibody (mAb) administered either as monotherapy, or in combination with other checkpoint inhibitors or other therapies. anti-PD-1/PD-L1 treatment progression is defined by meeting all of the following criteria:

- a) Has received at least 2 doses of an approved anti-PD-1/PD-L1 mAb.
- b) Has demonstrated disease progression after anti-PD-1/PD-L1 as defined by RECIST v1.1. The initial evidence of disease progression (PD) is to be confirmed by a second assessment no less than 4 weeks from the date of the first documented PD, in the absence of rapid clinical progression.^{1,2.}
- c) Progressive disease has been documented within 12 weeks from the last dose of anti-PD-1/PD-L1 mAb.
 - Seymour et al; iRECIST: Guidelines for response criteria for use in trials testing immunotherapeutics. Lancet Oncol 18: e143-52
 - ^{2.} This determination is made by the investigator. Once PD is confirmed, the initial date of PD documentation will be considered the date of disease progression.
- 6. Complete resolution of toxic effect(s) of the most recent prior chemotherapy to Grade 1 or baseline (except alopecia). If the subject received major surgery or radiation therapy of >30 Gy, they must have recovered from the toxicity and/or complications from the intervention.
- 7. Have an ECOG Performance Status of 0 or 1.
- 8. Demonstrate adequate organ function as defined by Table 1. All screening labs should be performed within 7 days prior to treatment initiation.
- 9. A female participant is eligible to participate if she is not pregnant or breastfeeding, and at least one of the following conditions applies:
 - Is not a WOCBP

OR

- Is a WOCBP and using a contraceptive method that is highly effective (with a failure rate of <1% per year), with low user dependency, or be abstinent from heterosexual intercourse as their preferred and usual lifestyle (abstinent on a long-term and persistent basis), as described in Section 5.7.2 during the intervention period and for at least 130 days after the last dose of study intervention and agrees not to donate eggs (ova, oocytes) to others or freeze/store for her own use for the purpose of reproduction during this period. The investigator should evaluate the potential for contraceptive method failure (ie, noncompliance, recently initiated) in relationship to the first dose of study intervention.
- A WOCBP must have a negative highly sensitive pregnancy test (urine or serum) within 24 hours before the first dose of study intervention.

Protocol/Amendment No.: 001-08

If a urine test cannot be confirmed as negative (eg, an ambiguous result), a serum pregnancy test is required. In such cases, the participant must be excluded from participation if the serum pregnancy result is positive.

- Additional requirements for pregnancy testing during and after study intervention are located in Section 5.7.2.
- The investigator is responsible for review of medical history, menstrual history, and recent sexual activity to decrease the risk for inclusion of a woman with an early undetected pregnancy.
- Contraceptive use by women should be consistent with local regulations regarding the methods of contraception for those participating in clinical studies.
- 10. Male subjects are eligible to participate if they agree to the following during the intervention period and for at least 130 days after the last dose of study intervention:
 - Refrain from donating sperm

PLUS either:

Be abstinent from heterosexual intercourse as their preferred and usual lifestyle (abstinent on a long-term and persistent basis) and agree to remain abstinent

OR

- Must agree to use contraception unless confirmed to be azoospermic (vasectomized or secondary to medical cause [Section 5.7.2]) as detailed below:
- Agree to use a male condom plus partner use of an additional contraceptive method when having penile-vaginal intercourse with a WOCBP who is not currently pregnant. Note: Men with a pregnant or breastfeeding partner must agree to remain abstinent from penile-vaginal intercourse or use a male condom during each episode of penile-vaginal penetration.

Contraceptive use by men should be consistent with local regulations regarding the methods of contraception for those participating in clinical studies.

- 11. HIV-infected subjects must meet these additional criteria:
 - Have HIV-1 infection documented by any licensed rapid HIV test or HIV enzyme or chemiluminescence immunoassay (E/CIA) test kit at any time prior to study entry (Day 1) and confirmed by a licensed Western blot or a second antibody test by a method other than the initial rapid HIV and/or E/CIA, or by HIV-1 p24 antigen, or plasma HIV-1 RNA VL.
 - Have well-controlled HIV on ART, defined as:
 - o must have a CD4+ T cell count >350 cells/mm3 at time of screening;
 - o must have achieved and maintained virologic suppression defined as confirmed HIV RNA level below 50 or the LLOQ (below the limit of quantification) using the locally available assay at the time of screening and for at least 12 weeks prior to screening;

Protocol/Amendment No.: 001-08

o must have been on a stable regimen, without changes in drugs or dose modification, for at least 4 weeks prior to study entry (Day 1).

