 - must have achieved and maintained virologic suppression defined as confirmed HIV RNA level below 50 or the LLOQ (below the limit of quantification) using the locally available assay at the time of screening and for at least 12 weeks prior to screening;

Protocol/Amendment No.: 001-08

- must have been on a stable regimen, without changes in drugs or dose modification, for at least 4 weeks prior to study entry (Day 1).

5.1.2.3 Subject Inclusion Criteria for Arm 3

In order to be eligible for participation in Arm 3 of this trial, the subject must meet the following inclusion criteria:

- 1. Be \geq 18 years of age on day of signing informed consent.
- 2. Voluntarily agreed to participate by providing documented informed consent. The subject may also provide consent for Future Biomedical Research. However, the subject may participate in the main trial without participating in Future Biomedical Research.
- 3. Have a histologically- or cytologically confirmed advanced/metastatic solid tumor or lymphoma by pathology report and who have received or have been intolerant to all treatment known to confer clinical benefit. Solid tumors and lymphomas of any type are eligible for enrollment. Tumor types of greatest interest include, but are not limited to, malignant melanoma, HNSCC, breast adenocarcinoma, and lymphomas.
- 4. Have Stage III or Stage IV disease that is not surgically resectable.
- 5. Has metastatic liver involvement that does not exceed one-third of the total liver volume in subjects to be treated by liver IT injection. Hepatocellular carcinoma subjects are excluded from eligibility of intratumoral liver injection. In addition, has at least one injectable liver lesion with the following:
 - The injectable liver lesion is amenable to image-guided intratumoral injection and biopsy via ultrasound guidance or cross-sectional imaging (CT/MRI).
 - Injectable lesion(s) must be ≥1 cm in longest diameter and ≤10 cm in longest diameter.
- 6. Have at least 1 distant and/or discrete noninjected lesion that is amenable to biopsy via visual inspection or amenable to biopsy via image guidance, such as ultrasound or CT/MRI. This lesion must be measurable as defined by the response criteria used to assess the subject (RECIST 1.1 for solid tumors or revised IWG criteria for lymphomas).
 - For RECIST 1.1, \geq 1 cm in longest diameter for non-nodal lesions, or \geq 1.5 cm in short axis for nodal lesions.

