5.2.5.2 Timing of MK-1454 Dose Administration in Part II - Expansion Cohorts

In Cohorts A and B, MK-1454 IT will be administered on Day 1, Day 8, and Day 15 in each 21-day cycle for Cycles 1 and 2. Beginning with Cycle 3, MK-1454 will be administered on Day 1 of each 21-day cycle.

Cohort C will initiate MK-1454 visceral IT treatment at the dose and frequency established as the RP2D from Arm 3.

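### Part II inclusion criteria 3 and 4 are inconsistent: as written, a Cohort C subject whose only injectable lesions are in the liver is ineligible

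*Combined protocol and SAP*

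**What the plan says.** Section 5.1.3 gives one numbered list for the three expansion cohorts.

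- **Criterion 3** carries no cohort or route qualifier. It opens with "Have at least one measurable lesion which is amenable to injection" and continues "This injectable lesion must meet one of the following criteria". The first option begins "A cutaneous or subcutaneous lesion ≥1 cm in longest diameter for solid tumors", with a short-axis threshold of 1.5 cm for nodes and an upper limit of 10 cm. The second begins "Multiple coalescing, superficial lesions which in aggregate have a longest diameter of" 1 to 10 cm. The list ends there.
- **Criterion 4** is conditional on route: "In subjects to be treated by liver IT injection, has metastatic liver involvement that does not exceed one-third of the total liver volume". It then asks for at least one injectable liver lesion of 1 to 10 cm that can be reached under image guidance.
- **Criterion 5** defines the cohorts. The entry for the third begins "Cohort C: Other anti-PD-1/PD-L1 treatment-naïve solid tumors with liver metastases" and does not mention superficial disease.

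On treatment, Section 5.2.5.2 states "Cohort C will initiate MK-1454 visceral IT treatment at the dose and frequency established as" the RP2D from Arm 3. For Arm 3 itself, criterion 5 of Section 5.1.2.3 requires that the subject "has at least one injectable liver lesion with the following" conditions. That is Arm 3's only criterion on the injectable lesion.

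**The concern.** Inclusion criteria are cumulative unless the text says otherwise. Section 7.1.1.2 has the investigator check all of them, and Appendix 12.1 makes meeting them a condition of enrolment. Criterion 3 offers no option that a liver lesion can satisfy, and criterion 4 adds a requirement without lifting criterion 3.

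A site that follows the text exactly must turn away subjects for whom Cohort C was created. A site that follows the evident intent enrols them and has an eligibility deviation to explain. Sites may choose differently, so the population behind the Cohort C response rate could depend on how each site reads the list.

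The efficacy analysis is also touched. Section 8.6.1 and the note in Section 3 pool Part I subjects into a Part II cohort if they meet the inclusion criteria for that tumour type and received the same dose level in combination. Whether criterion 3 counts among those criteria is not stated.

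**Working it through.** No formula or stated figure is involved. The check is to apply the criteria together and look for an exemption elsewhere.

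**1. The logic of the list.** As written, on the lesion and disease criteria:

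eligible = criterion 3 AND (criterion 4, if liver-injected) AND criterion 5.

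**2. Connectives.** Section 5.1.3 writes its connectives out where it wants them. It has an 'or' between the two options in criterion 3, an 'and' between the two conditions in criterion 4, and an 'or' between the two staging routes for Cohort A in criterion 5. Nothing joins criterion 3 to criterion 4. The words 'in addition' inside criterion 4 link the liver-volume limit to the injectable liver lesion; they do not make criterion 4 an alternative to criterion 3.

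**3. Cohort C subjects, case by case** (each assumed to meet criteria 4 and 5):

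- Liver lesion plus a qualifying cutaneous, subcutaneous or coalescing superficial lesion: criterion 3 met, eligible.
- Liver lesion plus a lymph node of at least 1.5 cm in short axis: unclear, because the text does not say whether the nodal threshold is confined to subcutaneous nodes.
- Injectable lesions in the liver only: criterion 3 not met, ineligible.
- Liver lesion plus only deep, non-nodal disease elsewhere, such as a pancreatic primary: criterion 3 not met, ineligible.

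**4. Comparison with Part I.** The two options in criterion 3 closely follow the first two lesion options for Arms 1 and 2 (Section 5.1.2.1), the cutaneous and subcutaneous arms. Criterion 4 closely follows the Arm 3 liver criterion (Section 5.1.2.3). In Part I these belong to separate lists, and each arm meets one of them. Part II puts both in one list.

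**5. Search for an exemption.** Section 4.2.1.2 names liver lesions as an injection site beside cutaneous, subcutaneous and nodal ones. Table 8 allows cross-sectional imaging guidance. Section 7.1.1.9 allocates Part II subjects by histology, eligibility and whether lesions can be reached. All of this fits liver injection in Cohort C, but none of it waives criterion 3.

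**6. Size.** Section 5.3 plans 60 subjects for Cohort C, out of 120 in Part II (60/120 = 50%) and about 235 overall (60/235 = about 26%). These are the numbers screened under the rule. If f is the share with injectable disease only in the liver, 60 × f would fail. The documents do not give f, so with f between 0 and 1 the range is 0 to 60.

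**7. Effect on the analysis sets.** The FAS (Section 8.5.3) requires measurable disease at baseline and a dose of study medicine, not full eligibility. A liver-only Cohort C subject who is enrolled anyway stays in the FAS. The pooling rule has two readings:

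- If the inclusion criteria for the tumour type mean the whole of Section 5.1.3, liver-only Arm 3 subjects fail criterion 3 and are not pooled.
- If they mean only the cohort definition in criterion 5, criterion 3 plays no part.

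**The case against.** The strongest reply is that the intent is plain. Criterion 4 addresses liver-injected subjects by name, sets its own lesion and size requirements, and comes from an arm where it is the sole lesion criterion. The injection guidance in criterion 3 covers only cutaneous and subcutaneous lesions. Nothing in the protocol explains why a liver-injected subject should need a second injectable lesion, and few sites would read it that way. This is a drafting gap, not a design anyone chose.

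That account of the intent stands, and it makes the correction uncontroversial. It does not make a liver-only subject eligible on the text.

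Other parts of the objection limit what can be claimed:

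- **Half of Part II is excluded.** A reader might infer this from 60 of 120. The documents support 60 only as an upper bound, since subjects with a qualifying lesion outside the liver pass.
- **Every Cohort C subject needs a superficial lesion as well as a liver lesion.** This is too firm, because the scope of the nodal threshold is not explicit.
- **The Cohort C response rate would mix Arm 3 subjects with a different population because of criterion 3.** This does not follow. If criterion 3 counts for pooling, pooled Arm 3 subjects must meet it too; if it does not count, it does not affect who is pooled. The literal reading can shrink the pool but does not create a mismatch. Arm 3 and Cohort C already differ on other entry criteria, including lymphoma and prior PD-1/PD-L1 treatment.
- **Deviations have already occurred.** The documents record none. Cohort C's dosing frequency is still to be determined in Table 8, and Section 2.1.2 opens Cohorts A and B first.

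**Conclusion.** The inconsistency is real. Read as a cumulative list, Section 5.1.3 makes a Cohort C subject with only liver injectable lesions ineligible, while the cohort definition, the assigned route and the Arm 3 precedent all point to that subject as one the cohort is meant to enrol. Because it is an operative entry rule that excludes intended subjects when followed exactly, it is more than a matter of style.

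The rule applies to screening of all 60 planned Cohort C subjects. The number who would actually fail is unknown; 0 to 60 is an assumption, not an estimate. The possible effect on the ORR is limited to liver-only Arm 3 subjects being left out of the Cohort C pool, and only if criterion 3 is read into the pooling rule. The conclusion rests on treating the numbered criteria as cumulative and on finding no exemption elsewhere in the documents.

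**What to change.** Reconcile criteria 3 and 4 of Section 5.1.3 before Cohort C opens. Either change is enough:

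- Add a third option to criterion 3: or, for subjects to be treated by liver IT injection, a measurable liver lesion meeting criterion 4.
- Limit the lesion list in criterion 3 to subjects not treated by liver injection. The opening requirement for a measurable injectable lesion stays for everyone.

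Both keep the measurability requirement, which criterion 4 does not state itself and which the FAS depends on. The cost is one line in a protocol amendment. Statistical methods, sample size, dose and schedule are unchanged, and the change removes criterion 3 as a reason to leave liver-only Arm 3 subjects out of the pool.

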4.2.1.2 Rationale for Part II - Expansion Cohorts

STING has been reported to be expressed in many human tissues and broadly across multiple human tumor subsets, including pancreatic adenocarcinoma, head and neck cancer, melanoma, colorectal cancer, TNBC, and other solid tumors. In addition, tumor type selection was based on projected accessibility for IT injection into cutaneous lesions, subcutaneous solid tumors, subcutaneous lymph nodes, and liver lesions. The selected subject populations for Expansion Cohorts represent an unmet medical need.

In preclinical studies intratumoral delivery of STING agonists leads to complete tumor regression or significant tumor growth inhibition in both anti-PD-1 -responsive and nonresponsive mouse syngeneic tumor models and can also induce immune-mediated clearance of noninjected tumors. In addition, tumor-bearing mice whose tumors completely regress through the action of a STING agonist become protected against subsequent challenges with the same tumor, indicating that induction of a durable tumor-specific T cell memory has occurred [4] [5] [6].

Existing and emerging, external and internal data suggest that the observed antitumor efficacy of STING agonism is primarily obtained through enhancing the capacity of the innate immune system to present tumor-associated antigens to CD8⁺ T cells as well as through a direct anti-proliferative effect on tumor cells.

Protocol/Amendment No.: 001-08

Based on preclinical data and mechanism of action of STING agonism, combination therapy of MK-1454 with the anti-PD-1 mAb pembrolizumab may demonstrate efficacy in patients who did not respond to pembrolizumab or are predicted to be poor responders based on gene expression profiling [22], PD-L1 expression and/or low tumor mutational burden. In these patients, a two-step process is hypothesized to occur, STING agonism-driven priming and initial expansion of antitumor CD8⁺ T cells and pembrolizumab-driven expansion of relevant tumor-specific T cells with prevention of T cell exhaustion.

Therefore, MK-1454 in combination with pembrolizumab may be beneficial for subjects with tumor types selected in the Expansion Cohorts, who have received or been intolerant to standard of care regimen(s).

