4.2.2.6 Rationale for Dose Schedule Expansion Cohorts A and B (Part II)

The starting dose for expansion Cohorts A and B will be the preliminary RP2D established in Arm 2, based on emerging safety, tolerability, and PK/pharmacodynamic data. The rationale for weekly dosing for the first 6 weeks (Cycle 1 and Cycle 2), followed by dosing every 3 weeks thereafter, is to allow for congruence of the dosing schedule of visceral intratumoral administration (Part I: Dose Escalation and Confirmation Arm 3) to the dosing schedule for cutaneous and subcutaneous intratumoral administration.

The starting dose and frequency for Cohort C will be the preliminary RP2D established in Arm 3.

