5.2.1.1.2 Dose Selection in Part II - Expansion Cohorts (Cohorts A and B)

The starting dose for Cohorts A and B is confirmed to be based on the safety, PK, and PD data from dose escalation and confirmation of MK-1454 IT in combination with pembrolizumab in Arm 2 (Table 8). The minimum number of lesions per subject per treatment visit to be injected is 1 lesion, and the maximum number of lesions to be injected per subject per treatment visit is 3 lesions. Each subject at this dose level will receive a fixed dose of intratumoral MK-1454 prepared in a volume of 1 mL to 3 mL of injectate, based on lesion size (see Table 9).

The starting dose for Cohort C will be the preliminary RP2D (both dose level and frequency) from the dose escalation and confirmation of MK-1454 visceral IT established in combination with pembrolizumab in Arm 3.

Dose volume for Expansion Cohorts will be determined by lesion size, as detailed in Table 9.

Protocol/Amendment No.: 001-08

Table 8 Trial Treatment for MK-1454 IT in Combination with Pembrolizumab Part II (Expansion Cohorts A, B, and C)

Drug, Vaccine, Biologic, Device, etc.	Dose/ Potency	Dose Frequency	Route of Administration	Regimen/ Treatment Period	Use
Pembrolizumab	200 mg	Q3W	IV infusion	Day 1 of each 21-day cycle	Experimental
MK-1454ª	Cohorts A and B: Colort C: Preliminary RP2D established in Arm 3	Cohorts A and B: CCI Cohort C: TBDb	Intratumoral Via visual inspection for cutaneous lesions, or via ultrasound or cross-sectional imaging (CT/MRI) guidance, as needed	Cohorts A and B: CCI Cohort C: TBDb	Experimental

CT = computed tomography; MTD/MAD = maximum tolerated dose/maximum administered dose; MRI = magnetic resonance imaging; QW = once each week; Q3W = once every 3 weeks; RP2D = Recommended Phase 2 Dose; TBD = to be determined.

Table 9 Injectate Volume for Arm 3 Visceral IT (Part I) and Expansion Cohorts (Part II)

Lesion Size (longest dimension)	Injection Volume
>5 cm	3 mL
>2.5 cm to 5 cm	2 mL
≥1.0 cm to 2.5 cm	1 mL

5.2.1.2 Accelerated Titration Design in Arms 1, 2, and 3

The initial dose escalation in Arms 1, 2, and 3 will proceed following an ATD.

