Single subjects will be enrolled into sequential dose levels with up to 300% dose increment increases from the previous dose, eg Dose ranges are outlined in Table 3, Table 4, and Table 5. Up to 3 subjects per cohort may be allowed in the event of simultaneous enrollment. The first 2 subjects who will receive MK-1454 treatment at a new dose level must be at least 7 days apart. The subsequent dose level to be tested in the next cohort of subjects will be communicated to the investigator or designee following each dose escalation decision meeting.

The dose for ending ATD will be the dose level at which one of the following occurs:

- The cohort is completed.
- ≥ Grade 2 toxicity as assessed by the investigator to be related, probably related, or possibly related to the drug according to NCI CTCAE v4.

^a MK-1454 will be administered within 0.5 to 4 hours following completion of pembrolizumab infusion.

^b Dose frequency will be determined in Arm 3.

Protocol/Amendment No.: 001-08

• Elevation of systemic TNF- α in blood above baseline levels by ≥ 3 -fold in a given subject during the first cycle of MK-1454 (Arm 1 and 2 only).

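### Part II does not limit liver injection to Cohort C, and for Cohorts A and B it states no condition that Arm 3 has cleared the dose and frequency

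*Combined protocol and SAP*

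**What the plan says.** **Eligibility.** Section 5.1.3 places the liver criterion in the general Part II list, ahead of the cohort-specific item 5: "In subjects to be treated by liver IT injection, has metastatic liver involvement that does not exceed one-third of the total liver volume". Item 3 of the same list requires at least one injectable cutaneous, subcutaneous, nodal or coalescing superficial lesion. It does not say that only such lesions may be injected. No exclusion in 5.1.5 bars liver injection in Cohort A or B.

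**Rationale.** Section 4.2.1.2 covers Part II as a whole: "tumor type selection was based on projected accessibility for IT injection into cutaneous lesions, subcutaneous solid tumors, subcutaneous lymph nodes, and liver lesions".

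**Route.** Table 8 splits the MK-1454 dose, frequency and regimen between Cohorts A/B and Cohort C, but gives one route entry for all three: "Via visual inspection for cutaneous lesions, or via ultrasound or cross-sectional imaging (CT/MRI) guidance, as needed".

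**Dose and schedule.** For Cohort C, 5.2.5.2 says: "Cohort C will initiate MK-1454 visceral IT treatment at the dose and frequency established as the RP2D from Arm 3". Section 5.2.1.1.2 agrees: "The starting dose for Cohort C will be the preliminary RP2D (both dose level and frequency) from the dose escalation and confirmation of MK-1454". The Cohort C frequency in Table 8 is still to be determined, with the footnote "Dose frequency will be determined in Arm 3". For Cohorts A and B the dose comes from Arm 2, and 5.2.5.2 says: "MK-1454 IT will be administered on Day 1, Day 8, and Day 15 in each 21-day cycle for Cycles 1 and 2". Nothing readable makes that regimen depend on lesion site. Section 2.1.2 opens Cohorts A and B before Cohort C.

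**The concern.** The protocol treats visceral injection as a separate risk. Section 4.2.2.4 starts it at Q3W because repeated visceral injection may be unsafe, and allows increases only as tolerance permits. Arm 3 then raises frequency and dose under the mTPI rules. Cohort C inherits the result of that staging.

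Cohorts A and B do not. An investigator who follows item 4, Table 8 and 5.2.5.2 literally could inject a liver lesion weekly for six weeks at a dose set in the cutaneous/subcutaneous arm. The opportunity is plausible. Cohort B takes metastatic TNBC and Cohort A takes Stage IVc HNSCC. During therapy, Appendix 12.3 ranks new or progressing lesions above those chosen for size, subject to safety and accessibility. Minimum observation after the first dose is 8 hours in Part II, against 24 hours inpatient in Part I (7.1.4.3).

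What is at stake is whether visceral dosing in Cohorts A and B stays inside the staging that the protocol set up for it.

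**Working it through.** The plan gives no figure of its own on this point. The check is a comparison of text, followed by a count of visits and volumes.

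**1. Is there a restriction or a condition?**

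| Place | Cohort C | Cohorts A and B |
|---|---|---|
| 5.1.3 item 4 (liver conditions) | applies | applies; no cohort named |
| Table 8 route (includes CT/MRI guidance) | applies | same entry |
| Source of dose (2.1.2, 5.2.1.1.2) | Arm 3, visceral | Arm 2, cutaneous or subcutaneous |
| Frequency (5.2.5.2) | from Arm 3 | Days 1, 8, 15 in Cycles 1 and 2 |
| Arm 3 clearance required | yes | none stated |

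The protocol does name a cohort where it wants a limit: exclusion 29 in 5.1.5 applies to Cohort C alone. Item 4 has no such label.

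**2. Visits in Cycles 1 and 2 (42 days).**

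- Cohorts A and B: 2 cycles × 3 visits = 6 (Days 1, 8, 15, 22, 29, 36).
- Arm 3 at its Q3W starting frequency: 2 × 1 = 2 (Days 1, 22).
- Arm 3 at its highest frequency: up to 2 × 3 = 6. Section 6.1.3 allows Day 8 and Day 15 dosing in Cycles 1 and 2 by cohort; the escalated frequencies themselves are redacted, so 6 is an assumption.
- Ratio of A/B to Arm 3: from 6/6 = 1 to 6/2 = 3.

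**3. Injectate into liver lesions over the same 42 days.** Table 9 serves both Arm 3 and the expansion cohorts (1 mL for 1.0 to 2.5 cm, 3 mL above 5 cm). The cap is 3 mL per visit in Cohorts A and B (4.2.2.5) and in Arm 3 (5.2.1.1.1).

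- Cohorts A and B, no liver lesion injected: 0 mL.
- Cohorts A and B, one liver lesion of 1.0 to 2.5 cm at every visit: 6 × 1 = 6 mL.
- Cohorts A and B, upper bound: 6 × 3 = 18 mL.
- Arm 3 at 2 visits: 2 × 1 = 2 mL to 2 × 3 = 6 mL.
- Arm 3 at 6 visits: 6 × 1 = 6 mL to 6 × 3 = 18 mL.

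At 6 visits the Arm 3 range equals the A/B range for a subject whose liver lesion is injected at every visit. Volume is not dose, and the MK-1454 doses are redacted, so the comparison cannot be taken to milligrams. The number of A/B subjects with an injectable liver lesion is not known.

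**The case against.** The readable text already points to a split by route. Only Cohort C is described as receiving visceral treatment. Item 3 resembles the Arms 1 and 2 criterion and item 4 the Arm 3 criterion, so Part II may simply have merged two route-specific rules. Item 4 is conditional: it limits subjects who are to have liver injection and does not authorise it in every cohort. Section 4.2.1.2 explains the choice of tumor types for Part II as a whole, and the shared route entry has to cover Cohort C. Read literally, item 3 gives every A/B subject a superficial or nodal target, and Appendix 12.3 prefers visible and palpable lesions. All of this stands as evidence of intent and makes the event less likely. None of it is a restriction.

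Redaction matters too. Figure 3 and the A/B dose, frequency and regimen entries in Table 8 cannot be read, and a limit might sit there.

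A reader might infer that Cohorts A and B would receive three times the visceral exposure of Arm 3. The documents do not support that. The factor of 3 applies only against the Arm 3 starting frequency. Section 4.2.2.6 justifies the A/B schedule by congruence between visceral and superficial dosing, so the ratio may well be 1.

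Nor does the undetermined Cohort C frequency show that Arm 3 had not cleared the A/B regimen. The NOAEL-based Arm 3 start described in 4.2.2.3 should not be overread either: the same sentence relies on combination safety already evaluated in Arm 2 to avoid repeating dose levels.

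General safeguards also exist: cohort opening staggered on Part I data, the one-third liver limit, observation after the first dose, safety teleconferences, and injection-site and CRS rules. They help, but none releases visceral dose or frequency stepwise.

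**Conclusion.** The point holds as a minor, inexpensive patient-safety improvement. The readable rules allow a liver lesion in a Cohort A or B subject to be injected at the Arm 2-derived dose, weekly through Cycles 1 and 2, without any stated condition that Arm 3 has cleared that dose and frequency. The likely intent was liver injection in Cohort C only.

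The size is a visit ratio between 1 and 3, possibly exactly 1, in an unknown and perhaps very small number of subjects. No excess exposure over Arm 3 is shown. The conclusion assumes that the unreadable parts of Table 8 and Figure 3 contain no limit by lesion site. Confidence is medium for that reason.

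**What to change.** Add one sentence to 5.2.1.1.2 and 5.2.5.2: a liver or other visceral lesion in a Cohort A or B subject may be injected only at a dose and frequency already cleared in Arm 3. If liver injection was never intended in those cohorts, label 5.1.3 item 4 and visceral injection in Table 8 as applying to Cohort C only. The clinical choice between the two is the sponsor's.

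Either change fits in the next amendment. The planned numbers stay at 30 + 30 + 60 = 120. With the conditional sentence, Cohorts A and B would have slightly fewer injectable lesions until Arm 3 clears the regimen; with the label, the loss would be permanent.
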